2.4.3. Inclusion criteria for patients

- Aged 18 or over (on date of invitation to participate)
- Three or more Long Term Conditions (LTC) from the following list: cardiovascular disease (CVD) or chronic kidney disease (CKD) (including coronary heart disease, hypertension, heart failure, peripheral arterial disease); stroke; diabetes; COPD or asthma; epilepsy; atrial fibrillation; severe mental health problems; depression; dementia; learning disability and rheumatoid arthritis.

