2.7. Sample size and justification

The study is designed to detect an effect size of 0.274 standard deviations in the primary outcome of the EQ5D-5L. Data about the variability of the new 5 level (5L) version of the EQ5D is currently more limited than for the well-established 3 level (3L) version. The standard deviation of the EQ5D-3L in the UK general population is 0.23, rising to 0.27 in the oldest respondents (aged over 75)³. Hence an effect size of 0.274 would equate to a detectable difference of (0.274*0.27) = 0.074 on the EQ5D-3L, previously deemed to be the minimum important difference (MID)⁴. Although less data is available about the variability in

the 5L version of the EQ5D than the 3L version, it seems wise to use this latest version of the EQ5D as it is likely to have greater sensitivity to change.

Based on data available from our previous studies, we estimate that 2.3% of adult patients will have multi-morbidity in terms of three or more LTCs as defined in this study. This equates to about 108 patients in an average sized practice of 6000 patients i.e. 3456 potentially eligible patients in 32 practices. Assuming 40% of patients agree to participate (n=1382), 80% are followed up to 12 months, and an Intra-Cluster Coefficient (ICC) of 0.03 for clustering at the practice level (based on the WISE trial)⁵ this sample provides around 90% power at a 5% significance level to detect an effect size of 0.274 standard deviations in the EQ5D measure between the intervention and control groups.

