6.6. Potential effect modifiers

Potential effect modifiers, selected *a priori* and informed by previous evidence, will be explored using appropriate interaction terms added to the regression models used for the primary analysis. Subgroup analyses of the primary outcome will explore differences in the effectiveness of the 3D intervention compared to usual care according to baseline measures of:

- Participant age (< median / ≥ median of consenting participants);
- Number of long term conditions as defined in section 2.4.3 (< median / ≥ median of consenting participants);
- Deprivation (quartiles of consenting participants);
- Depression alongside physical health problems (presence/absence).

Subgroup analyses are likely to be insufficiently powered since the trial was not powered to specifically test these effects. These subgroup analyses will therefore be hypothesis generating and will focus on interpretation of 95% confidence intervals rather than P-values.

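### The below-median subgroup for number of long-term conditions is empty if the median equals three, the entry minimum, and the SAP gives no fallback

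*SAP*

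**What the plan says.** Section 6.6 lists four baseline effect modifiers for the primary outcome and says they were selected a priori. The second is "Number of long term conditions as defined in section 2.4.3 (< median / ≥ median of consenting participants". The modifiers "will be explored using appropriate interaction terms added to the regression models used for the primary analysis". The same section is modest about their weight: "These subgroup analyses will therefore be hypothesis generating".

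Section 2.4.3, to which the subgroup definition points, requires for entry "Three or more Long Term Conditions (LTC) from the following list", and that list has eleven entries, some of which merge related diseases.

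The only information on how common such counts are is in section 2.7: "we estimate that 2.3% of adult patients will have multi-morbidity in terms of three or more LTCs as defined in this study". The SAP gives no distribution or expected median for the number of conditions, and no rule for a median that falls on the entry minimum.

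**The concern.** The subgroup variable and the entry criterion share one definition, so the variable has a hard floor at three. A cut that puts values equal to the median in the upper group works only if some participants lie strictly below the median. When the median sits on the floor, none do. The subgroup indicator is then constant and the model has no interaction to estimate.

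At stake is one pre-specified analysis. An analyst following the text would obtain no result and would have to choose another cut during the analysis. Age is split by the same rule but is far less exposed, because its floor is 18 and its median will not fall there in this population.

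**Working it through.** **The plan's own figure.** The SAP states no number for this subgroup. The planned sample size, used below as the denominator, comes from section 2.7 and is consistent with the stated power:

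- Patients: 108 × 32 = 3456; 3456 × 0.40 = 1382; 1382 × 0.80 = 1105.6 followed up.
- Per practice: 1105.6 / 32 = 34.55. Design effect: 1 + (34.55 − 1) × 0.03 = 2.0065. Effective N: 1105.6 / 2.0065 = 551.
- Power, two-sided 5%: Φ(0.274 × √(551/4) − 1.96) = Φ(3.216 − 1.960) = 0.895, against the stated figure of around 90%.

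**Step 1: the rule applied to a count with floor three.** Let p be the share of participants with exactly three conditions. If p > 0.5 the median is 3, and the number below 3 is zero whatever the rest of the distribution looks like. With N = 1382, and assuming for illustration that 70% of those above three have four conditions and 30% have five:

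| p (assumed) | Median | Below median | At or above median |
|---|---|---|---|
| 40% | 4 | 553 | 829 |
| 49% | 4 | 677 | 705 |
| 50% | 3.5 | 691 | 691 |
| 50.1% | 3 | 0 | 1382 |
| 60% | 3 | 0 | 1382 |
| 80% | 3 | 0 | 1382 |

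The rule goes from an almost even split to an empty group as p crosses one half.

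**Step 2: is p above one half?** The only anchor in the document is P(X ≥ 3) = 0.023 among adults. For each assumed count model, find the mean that satisfies this, then compute p = P(X = 3) / 0.023. Poisson example: the mean is 0.599, P(X = 3) = e^(−0.599) × 0.599³ / 6 = 0.0197, and p = 0.0197 / 0.023 = 0.855.

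| Assumed model for adults | p |
|---|---|
| Poisson | 85% |
| Negative binomial, size 2 | 77% |
| size 1 | 72% |
| size 0.5 | 65% |
| size 0.3 | 59% |
| size 0.2 | 54% |
| size 0.15 | 51% |
| size 0.13 | 49% |
| size 0.1 | 45% |

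Two-group Poisson mixtures matched to the same 2.3% also fall on either side of one half. With about 5% of adults at a mean of 2.5 conditions and the rest at 0.1, p is 47%. With about 4% at 2.5 and the rest at 0.3, p is 54%. Most of the models tried put the median at three; those with strong clustering of disease do not.

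**Step 3: the alternative cut.** Exactly three versus four or more gives 760/622 at p = 55%, 967/415 at p = 70% and 1106/276 at p = 80%. At a median of 3.5 or 4 it reproduces the planned split, for example 553/829 at p = 40%.

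**The case against.** The strongest reply is that the trigger is not shown. Only the 2.3% comes from the plan; every value of p comes from an assumed distribution, and the range crosses 50%. The models also describe all adults, whereas the cut uses consenting participants, who remain after exclusions, selection and an assumed 40% consent. The SAP does not say whether they have more or fewer conditions than other eligible patients. This stands, and it is why the point is conditional.

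A reader might infer that the analysis as written fails. The document does not support that: it fails only if more than half have exactly three conditions, and no distribution is given.

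A reader might also infer that a replacement cut would forfeit the a priori status that section 6.6 claims. That goes too far. The choice of modifiers would still be a priori. The cut-points were always to be taken from the sample, as medians and quartiles. The count is a baseline measure, so an empty group can be seen and repaired without outcome data. Section 2.8 aims to keep the junior statistician who analyses outcomes blinded, and section 8 requires amendments to be listed. These limit the harm, but none of them is a written fallback.

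Finally, the analysis is one of four that the SAP itself expects to be underpowered. That excuses low precision; it does not excuse a rule that may be impossible to carry out.

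**Conclusion.** The point holds in conditional form. The floor argument is exact and follows from sections 2.4.3 and 6.6 alone: a median of three empties the lower subgroup and makes the interaction inestimable, with no alternative specified. That the median will be three is likely across the assumed models (p from about 45% to 85%) but not established.

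The size is minor. One exploratory analysis of the primary outcome is exposed. The primary analysis, the sample size, the sensitivity analyses and the other three subgroups do not depend on it. It should be fixed, but nothing confirmatory rests on it.

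**What to change.** In section 6.6, before outcome data are examined, replace the median cut for number of conditions with exactly three versus four or more, and record the change in Table 10. The pooled baseline distribution of the count can be checked at the same time without reference to outcomes.

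The cost is one line of text. Nothing changes if the median is 3.5 or 4, and both groups are populated if it is 3. The one small downside is a less balanced split than the planned one if the median turned out to be five or more.

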6.7 Withdrawal rates

It is anticipated that a small number of patients will withdraw from each treatment group. Withdrawal refers to patients who actively decline further participation in the trial or are withdrawn by their practice (e.g. due to other illness, moving practice) and for whom there is no subsequent data collection. For each treatment group numbers and percentages of patients withdrawing will be reported along with reasons for withdrawal. Baseline characteristics will be compared between those who withdrew and those who did not in both treatment groups to look for differential withdrawal between the groups.

7. ANALYSIS OF SAFETY

In this population (older persons with multiple LTCs) a high number of adverse events (AE) are anticipated in both treatment groups, hence attention will be given only to serious adverse events (SAE) which may be related to the intervention or the research process (serious adverse reactions).

7.1. Serious adverse reactions

All reporting of SAEs of a related and unexpected nature will follow regulatory reporting requirements as set out in article 17 of the European Union Directive 2001. These will be reported to the sponsor immediately and will be reported to the REC within 7 days of the Trial Manager becoming aware of the event. Any relevant further information will be subsequently communicated within 8 days. In addition, all investigators will be notified. The TSC will be notified immediately of all SAEs thought to be treatment or research related. Potential SAEs which after review are not thought to be treatment or research related will be brought to the TSC's attention at their next scheduled meeting. The numbers and details of all SAEs will be reported to the Trial Management Group, Trial Steering Committee and Data Monitoring Committee.

For each treatment group the number and percentage of patients experiencing a serious adverse event, which appeared to be related to the intervention or the trial, will be reported. Given that patients with multimorbidity may be heavy users of secondary care services, new medical diagnoses, hospital admissions and deaths are expected and will not be considered as potential serious adverse events unless anyone involved in the study (participants, general practice staff or research staff) notify the research team of any events that they consider may have been related to the intervention or the research process. All deaths will be investigated for relatedness by requesting the patient's GP provide details of cause of death and relatedness to study.

If there are sufficient numbers of related SAEs, logistic regression with robust standard errors (to account for clustering) will be used to estimate the odds ratio (3D compared to usual care) for the different categories of SAEs. Corresponding 95% confidence intervals and P values will also be presented. If sufficient numbers of patients have multiple SAEs then ordered logistic models will be employed (e.g. outcome may be categorised as 0, 1, 2, 3+ SAEs).

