2.5. Description of interventions

The 3D intervention is a new approach to the management of patients with multi-morbidity. It is a complex intervention with four main components:

- Identification and prioritisation of patients with multi-morbidity identified patients will be given a '3D' card and their GP records 'flagged'.
- Improving patient-centred care each '3D' patient will be allocated a named usual GP and usual practice nurse who will have responsibility for co-ordinating their care. They will be offered longer appointments with their usual doctor or nurse when possible.
- Reducing the burden of illness and treatment '3D' patients will be offered a comprehensive assessment every 6 months instead of separate reviews for each of their LTCs. Each 3D assessment consists of 2 appointments approximately 1 week apart. At the first appointment, the patients' usual nurse will complete a bespoke computerised template to address all of the 3D elements (Dimensions of health, Depression and Drugs), collect relevant data in relation to the patient's combination of LTCs, and organise necessary tests. At the second appointment, the usual GP will review all the information, conduct a thorough review of medication and agree a written care plan with the patient for them to take away. Before the GP completes the 3D assessment a pharmacist will review each 3D patient's medication list and provide recommendations for the GP. This pharmacist review will be undertaken once during the year for each patient.

• Improving integration – each practice has a designated general physician who is readily available to discuss multi-morbidity patients with complex needs and help co-ordinate hospital investigations.

To ensure the intervention is effectively implemented, it will be incentivised as if it were an Enhanced Service or included in the Quality and Outcomes Framework (QOF), with payment against targets for completion of two 3D assessments per annum.

Practices allocated to the control arm will continue care as usual. In most practices this will mean patients are recalled to different clinics to see different practice nurses to review each of their long-term conditions.

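### If it is run, the odds ratio for related SAEs in SAP 7.1 will not estimate a difference in harm between 3D and usual care

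*SAP*

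**What the plan says.** Section 7 restricts the scope of the safety analysis: "attention will be given only to serious adverse events (SAE) which may be related to the intervention or the research process". Section 7.1 adds that "hospital admissions and deaths are expected and will not be considered as potential serious adverse events unless anyone involved in the study" notifies the team of an event they think may be related. Potential SAEs are then reviewed and separated into those thought related to treatment or research and those not. For every death, the patient's GP is asked about the cause and about relatedness to the study.

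Two outputs follow in section 7.1. The first is unconditional: the number and percentage of patients per arm with an SAE "which appeared to be related to the intervention or the trial, will be reported". The second is contingent: "If there are sufficient numbers of related SAEs, logistic regression with robust standard errors (to account for clustering) will be used", and its purpose is "to estimate the odds ratio (3D compared to usual care) for the different categories of SAEs". The SAP adds: "Corresponding 95% confidence intervals and P values will also be presented". Ordered logistic models are planned if enough patients have several SAEs.

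Section 2.5 describes the comparator: "Practices allocated to the control arm will continue care as usual". Section 2.8 states that participants and health care professionals cannot be masked.

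Two comparisons that do not depend on attribution appear elsewhere. Deaths are reported by arm, with a rate or hazard ratio to be considered (7.1.1). Number of hospital admissions is a secondary outcome (Table 2), modelled by random-effects Poisson regression (Table 6).

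**The concern.** An odds ratio between arms measures harm only if the outcome means the same thing in both arms. Here it does not. In the 3D arm a countable event is one attributed to 3D or to the research. In usual care it is one attributed to the research only, and a harm caused by usual care itself is not countable at all. The people who notify events know the allocation.

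The odds ratio therefore mixes any true effect on harm with the opportunity to attribute an event to 3D. It can exceed 1 when the all-cause risk is the same in both arms, and it gives no weight to harm that nobody attributed. Robust standard errors deal with clustering, not with this difference in definition. At stake is a harm estimate with a P value in the trial report that readers would take as a randomised comparison. The primary EQ5D-5L analysis is not affected.

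**Working it through.** **Figures in the plan.** The safety section states no SAE rate, event count or power. The only design figure is the power in section 2.7, used here just to confirm the planned size. Patients followed up per practice: 1382 × 0.8 / 32 = 34.55. Design effect: 1 + 33.55 × 0.03 = 2.0065. Effective number per arm: (1382 × 0.8 / 2) / 2.0065 = 552.8 / 2.0065 = 275.5. Power for 0.274 SD at two-sided 5%: 0.895, in line with the stated figure of around 90%. With 1:1 allocation of practices and an even split of patients (assumed), each arm has 1382 / 2 = 691 recruited patients.

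**Structure.** Let T be the all-cause SAE risk, equal in both arms (no true excess harm). Let r be the risk of an SAE judged research-related, also equal in both arms. Let s be the share of 3D-arm SAEs judged intervention-related after review. Treating the two kinds of related event as non-overlapping:

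- usual care: p0 = r
- 3D: p1 = r + s × T
- OR = [p1 / (1 − p1)] / [p0 / (1 − p0)]

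So p1 > p0, and OR > 1, whenever s > 0. If r may differ between arms, this holds unless r in usual care exceeds r in 3D by at least s × T.

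**Range.** T, r and s are all assumptions.

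| r | T | s | p1 | OR | Expected patients with a related SAE, 3D vs usual care (691 per arm) |
|---|---|---|---|---|---|
| 0.5% | 20% | 2% | 0.9% | 1.81 | 6.2 vs 3.5 |
| 0.5% | 20% | 5% | 1.5% | 3.03 | 10.4 vs 3.5 |
| 0.5% | 20% | 10% | 2.5% | 5.10 | 17.3 vs 3.5 |
| 0.5% | 30% | 2% | 1.1% | 2.21 | 7.6 vs 3.5 |
| 0.5% | 30% | 5% | 2.0% | 4.06 | 13.8 vs 3.5 |
| 0.5% | 30% | 10% | 3.5% | 7.22 | 24.2 vs 3.5 |
| 1% | 20% | 2% | 1.4% | 1.41 | 9.7 vs 6.9 |
| 1% | 20% | 5% | 2.0% | 2.02 | 13.8 vs 6.9 |
| 1% | 20% | 10% | 3.0% | 3.06 | 20.7 vs 6.9 |
| 1% | 30% | 2% | 1.6% | 1.61 | 11.1 vs 6.9 |
| 1% | 30% | 5% | 2.5% | 2.54 | 17.3 vs 6.9 |
| 1% | 30% | 10% | 4.0% | 4.12 | 27.6 vs 6.9 |

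Example, first row: p1 = 0.005 + 0.02 × 0.20 = 0.009; OR = (0.009 / 0.991) / (0.005 / 0.995) = 1.81. With s = 0 the OR is 1.0 throughout.

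A two-proportion calculation gives a rough chance of P < 0.05 of 10-24% at s = 2%, 33-71% at s = 5% and 76-98% at s = 10%. It ignores clustering and uses a large-sample approximation on small counts, so these figures show direction rather than size.

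**After the change.** Counting all SAEs regardless of attribution, with the same true risk T in both arms, the expected OR is 1.0.

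**The case against.** Several points on the other side stand.

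- **The model is contingent.** It is fitted only if related SAEs are numerous enough, and the unconditional output is descriptive. That limits how likely the problem is to arise. It does not remove it: what counts as enough is undefined, and the more events are attributed to 3D, the more likely the model is to be run.
- **Notification is not the same as counting.** Section 7.1 has a review step. Who reviews, and whether masked, is not stated here and may be in the protocol. Review can lower s; it cannot make an event in usual care related to an intervention that was not given.
- **Usual care is not structurally empty.** A reader might infer that control patients can have no countable event and that the odds ratio must be infinite. The SAP does not support this: research-related events count in either arm, and all deaths in either arm are checked for relatedness. An infinite or inestimable odds ratio is the limiting case r = 0, which a sensible reading of the numbers condition might well exclude.
- **Safety does not rest on this model alone.** A reader might infer that the trial could miss unattributed harm altogether. Deaths and admissions are compared without attribution, so the blind spot belongs to this odds ratio only.
- **The tilt runs against 3D.** With equal or higher research-related risk in the 3D arm, a spurious result would overstate harm. That is less worrying than hiding it, but still wrong to report with a P value.

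One might also read the categories of SAE in the model sentence as covering all SAEs. The sentence is conditioned on related SAEs, and section 7 limits attention to those "which may be related to the intervention or the research process (serious adverse reactions"), so this reading does not hold.

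**Conclusion.** The point holds, conditional on the model being run. The odds ratio and P value for related SAEs would not estimate a between-arm difference in harm, because the outcome has a component that only the 3D arm can supply. This follows from the SAP's definitions and needs no outside figure. The direction (expected OR above 1 with equal all-cause risk) requires that some events are attributed to 3D and that research-related events are not more common in usual care.

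The size rests on assumption: about 1.4 to 7 for T of 20-30%, r of 0.5-1% and s of 2-10%. A reader might take a single large value as the expected bias. The SAP gives no SAE or attribution rates, so only a range under stated assumptions can be defended. Nor should the alternatives be called unbiased. Under Table 2, admissions come from patient questionnaires where CSU data are unavailable, and under section 3.3 secondary outcomes are analysed complete-case. Their advantage is narrower: they do not depend on anyone judging relatedness.

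**What to change.** In section 7.1:

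- Keep the per-arm number and percentage of patients with a related SAE, with event details, as description only.
- Delete the logistic and ordered logistic comparisons, with their odds ratios, confidence intervals and P values.
- State that related SAEs are not compared between arms because intervention-related events can occur only in the 3D arm.

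In section 7, designate all-cause deaths (7.1.1) and number of hospital admissions (Tables 2 and 6) as the between-arm safety comparisons. Note beside the latter that admissions may be self-reported where CSU data are unavailable and that the analysis is complete-case.

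The cost is SAP wording and an entry in the amendment table. One contingent model and its ordered extension are dropped. No new data are needed, and both replacement comparisons are already provided for in the plan.

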7.1.1 Deaths

Given the population participating in the 3D trial, some deaths are expected before the end of follow-up in each treatment group. Numbers and percentages in each arm will be reported. Poisson regression and Cox regression with random effects will be considered (as appropriate) to calculate a rate ratio or hazard ratio with the corresponding 95% confidence intervals and P values. Models will also consider minimisation variables, age, number of long standing conditions, and EQ5D-5L at baseline.

